## Background

Leukemia is the most common malignant disease in children, of 30% of children under 15 years diagnosed with cancers caused by leukemia. In children with leukemia, 80% have acute lymphoblastic leukemia (ALL). ALL The highest cause of death in children with cancer.

The success rate of LLA patients reaches a remission of more than 90%, but 30-40% of them relapse in the maintenance phase. In developed countries, the last few years, the incidence of relapse to 11% . Meanwhile, the relapse rate in RSCM is still 28 , 7% . To achieve long-term remission, LLA patients require maintenance phase therapy for 2-3 years with mercaptopurin daily and low-dose methotrexate once a week. Drug toxicity during the maintenance phase is one of the main concerns not only because Can be life-threatening, but is a major cause of treatment discontinuation, which can increase the risk of relapse

During the maintenance phase, patients received 6-mercaptopurine therapy orally daily and low dose methotrexate week sekali. Mercaptopurine (6MP) is the main drug in this phase. The efficacy and toxicity of 6MP affected by enzyme activity TPMT. TPMT enzyme activity is influenced by the presence of genetic polymorphisms autosomal co-dominant populations variability etnik. existence of the gene encoding the enzyme permetabolisme medications will cause drug response differences between individuals, Which may affect treatment outcomes. To date there are 30 known variations of TPMT alleles. Wild type alleles, TPMT \* 1, show full enzyme activity. TPMT \* 2, \* 3A, \* 3B and \* 3C alleles are polymorphic alleles that are found in caucasian populations. All four variations of the allele showed decreased TPMT enzyme activity. Based on population studies, the distribution of TPMT enzyme activity in erythrocytes was trimodal; The majority of the population (89-94%) had a homozygous wild type allele exhibiting high TPMT activity, 6-11% had heterozygous mutant alleles with moderate TPMT activity, and 0.3% had homozygous mutant alleles showing low or undetectable TPMT activity.

Variations in TPMT enzyme activity due to polymorphism are the most important factors affecting intracellular 6TGN accumulation after 6MP administration. TPMT activity is inversely proportional to 6TGN concentrations in erythrocytes in LLA child patients. In homozygous wild type patients, their erythrocyte 6TGN levels are lower Compared with heterozygote mutant patients. Homozygous mutant patients had the highest 6TGN levels. Compared with homozygous wild type patients, heterozygous mutant patients required a lower 6MP dose, 30-50% of the standard dose, 22,31,36 but at risk Experienced severe myelosuppression. In homozygous mutant patients, the 6MP dose was reduced to 10-15 times less than the recommended dose, 28,37,38 because of the excessive accumulation of 6TGN in hematopoietic tissue, which may have life-threatening side-effects of myelosuppression.

The frequency and pattern of TPMT mutant alleles differ among different ethnic populations. In the American-Caucasian and African-American populations, all three mutant TPMT \* 2, \* 3A, \* 3C mutants are found, but the most mutant alleles in the US-Caucasian allele are TPMT \* 3A (3.2%), and in African-Americans TPMT \* 3C (2.4%). In the Southwest Asian (India and Pakistan), only 1% of the mutant alleles are TPMT \* 3A. In the Southeast Asian population, only 1% TPMT \* 3C mutant alleles were found. Similarly in populations in Thailand, Japan, and China, only TPMT \* 3C mutant alleles are found at 1-4.74%. The frequency and pattern of TPMT mutant alleles in the population of children with LLA in Indonesia is currently unknown

**Study Objectives:**

1. Knowing the distribution of TPMT \* 3A and \* 3C genotypes, 6TGN / 6meMP erythrocyte level, risk stratification, nutritional status, and albumin levels in LLA child patients in Indonesia.
2. Analyzing the association of hematotoxicity with TPMT \* 3A and \* 3C genotypes, erythrocyte 6TGN / 6meMP ratio, risk stratification, nutritional status, and albumin levels in the LLA child population in Indonesia.
3. Analyze the genotype associations of TPMT \* 3A and \* 3C with 6TGN / 6meMP erythrocyte ratio in LLA child.

**Study Design:**

This study used an observational, cross sectional study to obtain data on patient demographics, nutritional status, albumin levels, TPMT genotype, and 6TGN / 6meMP levels in LLA children.

## Statistical Analysis Plan (SAP)

Data is presented in the form of narration, tables or graphs. Subject characteristics data, TPMT polymorphism frequency, hematology effect, TGN and 6-meMP concentration, and TGN/6-meMP ratio in erythrocytes are presented descriptively, in mean (standard deviation), or median value (range of values) And in percentages.

To assess the relationship of TPMT polymorphism with 6TGN/6meMP ratio in erythrocytes using unpaired t test (normal distribution) or Mann Withney (abnormal distribution):

Genotype	Ratio TGN/6meMP (mean)		p-Value
	Wild type	Mutant	

To assess the association of hematologic toxicity with factors that may affect it:

	Variables	Hematotoxicity		p-value	OR	95% CI
		+	-			
		(Grade 1–4)	(Grade 0)			
Genotypea	- Wild type - Mutan					
Phenotypeb	6TGN/6meMP Ratio					
Risk	- High risk					
Stratificationa	- Standard risk					
Nutritional Statusa	- poor - normal-over weight					
Albumin levelsa	- Hypo - Normal					

OR= *odd ratio*; CI= confidents interval

a Statistical method:  $\chi^2$  test or Fischer test

b Statistical method: unpaired t test (normal distribution) or Mann Withney (abnormal distribution):

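### The five hematotoxicity factors are tested one at a time with no adjusted analysis, so the ORs are crude and cannot separate one factor from another

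*Combined protocol and SAP*

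**What the plan says.** Objective 2 (Study Objectives) asks for the association of hematotoxicity with the TPMT genotypes and with "erythrocyte 6TGN / 6meMP ratio, risk stratification, nutritional status, and albumin levels in the LLA child population in Indonesia". The Study Design section states: "This study used an observational, cross sectional study to obtain data on patient demographics", followed by the other study variables.

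The Statistical Analysis Plan serves this objective with a single table, introduced by "To assess the association of hematologic toxicity with factors that may affect it". Toxicity is split into Grade 1–4 against Grade 0. There is one row per factor, with columns for p-value, OR and 95% CI. Footnote a gives chi-square or Fisher for genotype, risk stratification, nutritional status and albumin. Footnote b gives, for the 6TGN/6meMP ratio, "unpaired t test (normal distribution) or Mann Withney (abnormal distribution").

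The available text names no regression model, stratified analysis or covariate, and no rule for choosing variables for a model. Subject characteristics are to be described but are given no role as covariates.

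**The concern.** In an observational study nothing balances the five factors against each other. If two are correlated, the crude OR for one carries part of the association that belongs to the other. Nutrition and albumin are the natural example, although the documents do not say that they are related. A factor with no association of its own could then show a raised OR, or a real association could be masked. The table's introduction speaks of factors that may affect toxicity, which invites reading each OR as a contribution. With no adjusted estimate beside the crude one, a reader cannot tell which case applies.

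A second problem needs no assumption. The ratio row has OR and 95% CI columns, but a t test or Mann-Whitney test compares two groups on a continuous measure and yields no OR. The SAP cannot complete its own table for that factor.

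**Working it through.** **Text check.** There is no planned figure to reproduce, because the documents give no sample size, power, event count or correlation. Each named method relates toxicity to a single factor, so every OR they can produce is crude. They produce an OR for four of the five factors.

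**Illustration of size.** Every input here is assumed: 30% of children poorly nourished; 50% toxicity in the others; nutrition-toxicity OR 3, so toxicity in the poorly nourished is 3/(1+3) = 75%; no albumin effect once nutrition is known; 100 to 200 children.

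Let a1 and a0 be the proportions with low albumin among poorly and well nourished children. The share poorly nourished is 0.3·a1/(0.3·a1 + 0.7·a0) among low-albumin children, and 0.3(1−a1)/[0.3(1−a1) + 0.7(1−a0)] among the rest. Toxicity in each albumin group is share × 0.75 + (1 − share) × 0.50. The crude albumin OR is the ratio of the two odds.

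Worked case, 50% against 10% low albumin (OR 9):
- Low albumin: share 0.15/(0.15 + 0.07) = 0.682; toxicity 0.6705; odds 2.035.
- Normal albumin: share 0.15/(0.15 + 0.63) = 0.192; toxicity 0.5481; odds 1.213.
- Crude OR = 2.035/1.213 = 1.68, where the true conditional OR is 1.

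The false-positive rates for albumin come from 20,000 simulated studies per setting. Each pair is N=100, then N=200.

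| Nutrition-albumin OR | Crude albumin OR | Chi-square | Continuity-corrected | Stratified by nutrition (Mantel-Haenszel) |
|---|---|---|---|---|
| 1 (none) | 1.00 | 5.2%, 4.9% | 2.6%, 3.1% | 4.8%, 4.9% |
| 1.95 (30% vs 18%) | 1.17 | 5.7%, 7.2% | 3.2%, 4.7% | 4.8%, 5.0% |
| 4 | 1.39 | 9.3%, 14.7% | 5.4%, 10.7% | 4.6%, 4.8% |
| 9 (50% vs 10%) | 1.68 | 17.2%, 30.3% | 10.9%, 24.0% | 4.6%, 4.8% |

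**Sensitivity.** With a nutrition-toxicity OR of 2, the crude albumin ORs in the last three rows fall to 1.11, 1.24 and 1.40. At OR 3, varying poor nutrition over 15–45% and toxicity over 30–70% gives 1.09–1.19 in the second row and 1.43–1.71 in the last.

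**The reverse direction.** Let nutrition have no effect given albumin, with low albumin in 40% against 10%, albumin OR 3, and 40% toxicity at normal albumin. Toxicity at low albumin is 2/(1+2) = 66.7%. The nutrition groups then have 0.4 × 0.667 + 0.6 × 0.4 = 50.7% and 0.1 × 0.667 + 0.9 × 0.4 = 42.7% toxicity, a crude nutrition OR of 1.38.

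**Price of adjusting.** By the approximation 1/√(1−φ²), where φ is the nutrition-albumin correlation, the albumin interval widens on the log scale by about 1% at OR 1.95 (φ = 0.134) and 12% at OR 9 (φ = 0.442).

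**Genotype.** The Background reports for Thai, Japanese and Chinese populations that *3C "mutant alleles are found at 1-4.74"%; it gives the Indonesian frequency as unknown. Assuming Hardy-Weinberg proportions, carriers = N[1 − (1−q)²]: about 2 to 9 at N=100 and 4 to 19 at N=200. With 50% toxicity, 2 carriers in 100 give a log-OR SE of √(1/1 + 1/1 + 1/49 + 1/49) = 1.43, so the 95% CI spans a factor of exp(1.96 × 1.43) ≈ 16 either way. With 18.5 carriers in 200 the SE is 0.49 and the factor about 2.6.

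**The case against.** The objective says association, and a crude OR answers that correctly. No section claims to identify independent factors, and the table's introduction is hedged. This stands: the crude table is not wrong and should stay. The gap is that nothing labels it unadjusted or lets a reader see whether an association survives adjustment.

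The nutrition-albumin link is assumed. The link the documents do state runs from genotype to 6TGN ("Variations in TPMT enzyme activity due to polymorphism are the most important factors affecting intracellular 6TGN accumulation after 6MP administration") and on to toxicity ("because of the excessive accumulation of 6TGN in hematopoietic tissue, which may have life-threatening side-effects of myelosuppression"). That is mediation, not confounding. This also stands, and it is a reason to keep genotype and ratio in separate models. The size is uncertain too: at a nutrition-albumin OR near 2 the error rate is close to nominal, and a nutrition-toxicity OR of 2 softens every row.

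If albumin reflects nutrition, adjusting for it removes part of nutrition's own association, so the adjusted nutrition OR can mislead in turn. That needs a caveat beside the estimate.

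Finally, a model adds least for genotype, the factor at the centre of the study, and its feasibility cannot be judged without N. With only 2 carriers at 50% toxicity, both fall in the same toxicity column half the time, and the unpenalised OR is then zero or infinite. This limits what can be said about genotype. It does not remove the case for risk group, nutrition and albumin.

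The empty OR cells in the ratio row are a separate matter. A single-factor logistic model would fill them, and they lend no weight to the confounding argument.

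**Conclusion.** The concern holds. The plan yields only crude ORs from an observational study, and its named test cannot supply the OR or interval for the ratio row. Both facts follow from the text alone.

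The size of any confounding cannot be derived from the documents. Under the stated assumptions it runs from none (OR 1.00, 5% false positives) to material (OR 1.68, 17–30%), depending on correlations and effect sizes the plan does not give. The crude table cannot show where this study lies in that range; an adjusted column would help to. This is a worthwhile, inexpensive improvement and not a flaw that invalidates the planned descriptive results.

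**What to change.** In the SAP:
- Keep the present table and label its ORs unadjusted.
- Add one pre-specified logistic model for Grade 1–4 against Grade 0 with genotype, risk stratification, nutritional status and albumin (continuous where the value is available). Use Firth penalisation, and state in advance which terms are dropped if events or mutant carriers are sparse. Add age and sex only if they are recorded and event counts allow.
- Fit a second model with the 6TGN/6meMP ratio in place of genotype, because the ratio lies on the path from genotype to toxicity. For the ratio row, report a crude OR from a single-factor logistic model and the adjusted OR from this model, and state the unit to which each refers.
- Report crude and adjusted ORs with 95% CIs side by side, and draw any statement about independent factors from the adjusted ones. Note that adjusting nutrition for albumin may remove part of nutrition's association.

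The cost is SAP wording and modest analysis time on factors the table already needs. Intervals widen, by roughly 1–12% for albumin in the illustration. The genotype estimate will stay imprecise if carriers are few; penalisation makes it finite but adds no information.
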